## **8.7 Photography sub-study analysis**

Participants consenting to participation in the photography sub study will have three sets of joint measurements at baseline and at 3, 6, 12 and 24 months post treatment; measurements obtained using a goniometer, measurements obtained using photographs taken in clinic, and measurements obtained using photographs taken by participants at home. The primary goal of the photography sub study is to assess the agreement between measurements obtained using a goniometer and measurements obtained using the photographs taken by participants at home, in order to determine whether the two methods of measurement might feasibly be used interchangeably. The photography sub study will also include a number of additional analyses investigating agreement between goniometric measurements and measurements obtained using patient photos following treatment, agreement between goniometric

measurements and measurements obtained using photos taken in clinic, and predictors of agreement (image quality and time elapsed between each type of measurement).

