### 8.7.1 Primary sub-study analysis

The primary sub-study analysis will investigate the agreement between the mean of the three measurements obtained using goniometer at baseline, and the measurement obtained using patient photographs at baseline (or patient photographs taken prior to treatment if baseline photos are unavailable). We will calculate separate 95% limits of agreement for the MCP and PIP joints of participants' reference digits. A range of plots will be used to assess the extent to which the assumptions of these analyses are met. If there is evidence of a relationship between the differences of the two measurements and their magnitude, then steps will be taken to account for this relationship using regression methods [13]. The calculation of the limits of agreement assumes that the differences are approximately normally distributed. The extent to which this assumption is met will be assessed by inspection of a normal quantile-quantile plot. Should there be extreme departures from normality then a non-parametric approach will be used as described in [13]. The differences between the two types of measurement will be plotted against their average, with the estimated limits of agreement overlaid. The extent to which agreement varies by digit will be investigated by generating separate limits of agreement and plots by digit (little, ring or middle/index/thumb). If feasible, the extent to which agreement varies according to image quality will be investigated by generating separate limits of agreement and plots by image quality category. The extent to which time between measurements explains variation in agreement will be explored by regressing the observed differences on the magnitude of the measurements (i.e. the average of the measurements obtained using each method) and the time elapsed between the two measurements.

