### 8.7.2 Secondary sub study analyses

Secondary analyses of the photography sub study will use similar techniques as described for the primary sub study analysis to assess the agreement between goniometric measurements and measurements obtained using participant photographs at the 3 and 6 month post treatment time points. Similar techniques will again be used to assess the agreement between baseline goniometric measurements and measurements obtained using photographs taken in clinic at baseline.

[figure not shown]

[figure not shown]

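### The time check in the photography sub-study can show a shift in mean difference as the gap between readings grows, but not limits of agreement that widen with it

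*SAP*

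**What the plan says.** SAP section 8.7 lists, among the aims of the sub-study, "predictors of agreement (image quality and time elapsed between each type of measurement"). Section 8.7.1 sets the agreement measure: "We will calculate separate 95% limits of agreement for the MCP and PIP joints of participants' reference digits".

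The candidate predictors are then handled in two ways.

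- **Digit and image quality:** separate limits and plots for each group. For image quality this means "generating separate limits of agreement and plots by image quality category", if feasible.
- **Elapsed time:** one regression. How far "time between measurements explains variation in agreement will be explored by regressing the observed differences on the magnitude of the measurements". Magnitude is taken as the mean of the two methods' readings, and the gap between them enters as the second covariate.

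Regression methods for limits that are not constant are also planned, but the trigger is "If there is evidence of a relationship between the differences of the two measurements and their magnitude". Elapsed time does not trigger them. The one plot of the differences that is named has the average of the two methods on its horizontal axis. The other plots serve to check the assumptions of the limits.

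Section 8.7.2 says that the secondary analyses "will use similar techniques as described for the primary sub study analysis to assess the agreement" at 3 and 6 months, and between baseline goniometry and baseline clinic photographs.

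**The concern.** The question asked is whether time explains agreement. The model fitted answers a narrower one: whether the average difference moves with time. If a longer gap makes home photograph and goniometer differ more in both directions, the positive and negative differences offset each other. The time coefficient then stays near zero while the limits widen.

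Gaps will vary. Section 5.10 asks participants to take the home photograph soon after the baseline visit, not at it. Section 8.7.1 also accepts a substitute ("or patient photographs taken prior to treatment if baseline photos are unavailable"), and section 2 allows up to 18 weeks from randomisation to treatment.

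The sub-study is meant to judge whether the two methods could be used interchangeably. If the limits come out wide, readers will want to know how much is due to the method and how much to timing. A flat time coefficient cannot settle that, and it could be mistaken for evidence that timing plays no part.

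**Working it through.** **Step 1. What the planned model estimates.** Write D for the difference, A for the average of the two methods and T for elapsed time. The plan fits E(D) = b0 + b1·A + b2·T. The limits at gap T are E(D) ± 1.96·s(T), where s(T) is the SD of D at that gap. The test of b2 = 0 concerns the centre of the limits. It says nothing about s(T).

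Example: b2 = 0 and s rises from 5 to 10 degrees. The half-width goes from 1.96 × 5 = 9.8 to 1.96 × 10 = 19.6 degrees, so the full width goes from 19.6 to 39.2 degrees. The coefficient under test is still zero.

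**Step 2. Inputs for a size check.** The SAP gives no sub-study size, SD of differences or gap distribution, so there is no figure to reproduce. All of the following are assumptions:

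- N from 50 to 400, and the gap rescaled to 0–1.
- Gaps either uniform or right-skewed (exponential with mean 0.25, capped at 1).
- SD of 5 degrees at zero gap, then constant or rising linearly to 10 degrees at the longest gap.
- Mean drift of 0 or 5 degrees at the longest gap.
- Two-sided 5% tests and 4,000 simulated studies per cell. The Monte Carlo standard error at 5% is √(0.05 × 0.95 / 4000) = 0.34 percentage points.

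Two tests of the time slope are compared: the planned regression of D on A and T (ordinary standard errors), and a regression of the absolute residuals from that model on A and T (robust standard errors).

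**Step 3. Rejection rates (%).**

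| Gaps | Scenario | Test | N=50 | 100 | 200 | 400 |
|---|---|---|---|---|---|---|
| Uniform | No time effect | Planned | 5 | 5 | 6 | 5 |
| | | Absolute residuals | 7 | 5 | 6 | 5 |
| Uniform | SD 5 to 10, no drift | Planned | 5 | 5 | 6 | 6 |
| | | Absolute residuals | 38 | 68 | 95 | >99 |
| Uniform | Drift 5, SD 5 | Planned | 51 | 82 | 98 | 100 |
| | | Absolute residuals | 6 | 6 | 5 | 5 |
| Uniform | Drift 5, SD 5 to 10 | Planned | 27 | 45 | 75 | 96 |
| | | Absolute residuals | 38 | 67 | 94 | >99 |
| Skewed | No time effect | Planned | 4 | 6 | 5 | 5 |
| | | Absolute residuals | 10 | 8 | 6 | 5 |
| Skewed | SD 5 to 10, no drift | Planned | 12 | 12 | 12 | 13 |
| | | Absolute residuals | 27 | 46 | 78 | 98 |
| Skewed | Drift 5, SD 5 | Planned | 35 | 62 | 89 | >99 |

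**Step 4. Reading the table.** The two tests see different things. The planned one responds to drift, and the other to spread. With skewed gaps and widening spread the planned test rejects in 12 to 13%. This does not grow with N, and it falls to 5 to 7% with robust standard errors. It is therefore inflated type I error for bias, not power for spread.

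**Step 5. Other settings.** With spread rising from 4 to 8 degrees, uniform gaps and no drift, separate simulations give 5 to 6% for the planned test against 37%, 68% and 93% for absolute residuals at N = 50, 100 and 200. For a smaller rise, from 5 to 8 degrees, the figures are about 5% against 19%, 37% and 69%. With skewed gaps the separate runs inflated the planned test to about 7 to 10%, so the degree of inflation depends on what is assumed.

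**The case against.** A reader might infer that the planned regression has no power to detect agreement getting worse as the gap grows. The documents do not support that. Limits of agreement have a centre as well as a width, and a bias that grows with the gap is also worsening agreement. The planned regression detects it well: 82% at N = 100 for a 5-degree drift with SD 5. Drift is plausible too, because sections 8.2.1 and 8.3.2 anticipate disease progression between baseline and treatment. When drift and widening occur together, the planned test still rejects in 27% to 96% of studies over N = 50 to 400. All of this stands, and it limits the point to widening scatter.

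Other objections, and what remains of them:

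- The SAP does not call the differences signed. That is inferred, but it is the natural reading, since the same differences feed the limits, the normality check and the plot.
- Digit and image quality are categorical and time is continuous, so a regression for time is an ordinary choice. That is fair. The gap in the plan is that only the mean is regressed.
- The analysis is exploratory, with no threshold or decision rule. A misreading of a null coefficient is a risk, not a certainty.
- Section 8.7.2 promises similar techniques without naming the time regression, so the carry-over to 3 and 6 months is likely but not stated. For baseline clinic photographs the gap should be small.
- A reader might also infer that the main trial's use of photographs depends on this check. It does not: sections 8.4.7 to 8.4.10 supplement goniometry with photographs without any condition on sub-study agreement.

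**Conclusion.** The point holds as a limited, cheap improvement. The single regression planned for elapsed time tests for a shift in mean difference and cannot show limits of agreement that widen with the gap. Nothing else in the SAP fills that space. This follows from the form of the model and needs no assumed numbers beyond reading the differences as signed.

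The size of the loss is illustrative only. With spread doubling, no drift and uniform gaps, the planned test stays at its error rate, while the added regression rejects in 38% to 95% of studies between N = 50 and 200. Skewed gaps, which the instruction to photograph soon after the visit makes plausible, reduce that to 27% to 78%. The sub-study's overall limits of agreement, the non-inferiority result and all other main-trial conclusions are unaffected.

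**What to change.** In section 8.7.1, and wherever the technique is reused under section 8.7.2:

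1. Keep the regression of the differences on magnitude and elapsed time, label it as the check of bias over time, and use robust standard errors.
2. Add a regression of its absolute residuals on magnitude and elapsed time, as the check of spread over time.
3. Report limits of agreement as a function of the gap, for example at zero and at the median gap. If the residuals are roughly normal, the mean absolute residual is SD × √(2/π). The limits are then the fitted mean difference ± 1.96 × √(π/2) = 2.46 times the fitted absolute residual. Limits by gap category would be a simpler alternative.
4. Base any statement about time and agreement on both regressions.

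The cost is a few lines of SAP text and one more exploratory coefficient, from data already being collected. The added test may be somewhat liberal in small samples with skewed gaps (10% at N = 50 and 8% at N = 100 in the runs above), and the report should say so.

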### 8.7.2 Secondary sub study analyses

Secondary analyses of the photography sub study will use similar techniques as described for the primary sub study analysis to assess the agreement between goniometric measurements and measurements obtained using participant photographs at the 3 and 6 month post treatment time points. Similar techniques will again be used to assess the agreement between baseline goniometric measurements and measurements obtained using photographs taken in clinic at baseline.

[figure not shown]

[figure not shown]

## 9. SAP amendment log

Amendment/addition to SAP and reason for change	New version number, name and date

## Appendix A – Participant Flow Diagram

## Appendix B – Data collection schedule

Data will be collected using participant and investigator CRFs

Data Collected	Baseline	Treatment Delivery	2 Weeks Post Treatment	6 Weeks Post Treatment	3 Months Post Treatment	6 Months Post Treatment	12 Month Post Treatment	24 Months Post Treatment
Patient Reported								
PEM	X	X			X	X	X	X
URAM	X				X	X	X	X
MHQ	X						X	X
EQ-5D-5L	X		X	X	X	X	X	X
SANE	X		X	X	X	X	X	X
Treatment Preference	X							
Overall Hand Assessment					X	X	X	X
Resource Use					X	X	X	X
Demographics and Medical History								
Demographics	X							
Comorbidity	X							
Concomitant Medications	X							
Condition Details and Clinical Assessment								
Condition History	X							
Diathesis Indicators	X							
Clinical Assessment	X							
Photography								
Clinician Photographs	X	X			X	X	X	X
Participant Photographs	Y	Y			Y	Y	Y	Y
Treatment Pathway								
Randomisation	X							
Treatment Delivered		X			X			
Clinical Outcomes								
Joint Measurements	X	X			X	X	X	X
Complications		X			X	X	X	X
Further Procedures					X	X	X	X
Safety Data								
Contraindications	X	X						
Adverse Events		Y	Y	Y	Y	Y	Y	Y

X = Mandatory data collection, Y = Conditional/triggered data collection

## Appendix C – MHQ scoring procedure

- The second item in the pain scale for each hand (MHQ34 and MHQ39) is reversed scored so that 1 = 5, 2 = 4, 4 = 2, 5 = 1
- The second item in the aesthetics scale for each hand (MHQ43 and MHQ47) is reverse scored so that 1 = 5, 2 = 4, 4 = 2, 5 = 1.
- If 50% or more of the items in a given scale are missing then a score for this scale cannot be validly calculated and should be considered missing.
- If strictly less than 50% of the items in a given scale are missing then these should be imputed with the mean of the non-missing items in that scale.
- A raw score for each scale is obtained by summing the responses in that scale.
- The raw scores are normalised to a range 0 - 100 following the procedure described in the table below.
- For the activities of daily living scale, the final scale score is the average of the one handed and two handed scores. For all other scales the final scale score is just the normalised score.

Scale	Items	Raw Score* (x)	Normalisation**	Scale Score***
Overall Hand Function				
Right	1, 2, 3, 4, 5	$5 \leq x \leq 25$	$y = 5 \times (25 - x)$	y
Left	6, 7, 8, 9, 10	$5 \leq x \leq 25$	$y = 5 \times (25 - x)$	
Activities of Daily Living				
Right	11, 12, 13, 14, 15	$5 \leq x \leq 25$	$y = 5 \times (25 - x)$	$\frac{y + z}{2}$
Left	16, 17, 18, 19, 20	$5 \leq x \leq 25$	$y = 5 \times (25 - x)$	
Both	21, 22, 23, 24, 25, 26, 27	$7 \leq x \leq 35$	$z = \frac{25}{7} \times (35 - x)$	
Work				
Both	28, 29, 30, 31, 32	$5 \leq x \leq 25$	$y = 5 \times (x - 5)$	y
Pain				
Right	33, 34, 35, 36, 37	$5 \leq x \leq 25$	$y = 0$ if item 33 = 5 $y = 5 \times (25 - x)$ otherwise	y
Left	38, 39, 40, 41, 42	$5 \leq x \leq 25$	$y = 0$ if item 38 = 5 $y = 5 \times (25 - x)$ otherwise	
Aesthetics				
Right	43, 44, 45, 46	$4 \leq x \leq 20$	$y = \frac{25}{4}(x - 4)$	y
Left	47, 48, 49, 50	$4 \leq x \leq 20$	$y = \frac{25}{4}(x - 4)$	
Satisfaction				
Right	51, 52, 53, 54, 55, 56	$6 \leq x \leq 30$	$y = \frac{25}{6}(30 - x)$	y
Left	57, 58, 59, 60, 61, 62	$6 \leq x \leq 30$	$y = \frac{25}{6}(30 - x)$	

\* For pain scale a higher score indicates more pain. For the other five scales a higher score indicates better hand performance.

\*\* A total MHQ score is obtained by taking the mean of the six scale scores, after reversing the score for the pain scale. The pain scale score is reversed by subtracting this score from 100.

\*\*\* The total MHQ score will be considered missing if any of the six scale scores are missing.

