### 8.2.3 Primary analysis model specification and fitting

The model fitted for the primary analysis will include all post treatment PEM scores as outcomes, modelling these using a covariance pattern model. This model will be comprised of three levels with post treatment measurement occasions ( $i = 1, 2, 3, 4$ ), nested in participants ( $j$ ), nested in centres ( $k$ ). Details of the terms included in the model are given in Table 2.

**Table 2:** Terms included in the primary analysis models. Fixed effect terms for treatment by time interactions will also be included.

Term	Interpretation	Type	Details
$\text{treat}_{jk}$	Randomised treatment group (collagenase or surgery) of the $j$ th participant at recruitment site $k$	Binary fixed effect	Indicator variable Surgery = 0, Collagenase = 1
$\text{time}_i$	$i$ th post randomisation time point	Categorical fixed effects	4 levels ( $i = 1, \dots, 4$ ) Included in model via 3 dummy indicator variables.
$\text{baseline}_{jk}$	Baseline PEM score of the $j$ th participant at recruitment site $k$ (assumed linear relationship with outcome)	Continuous fixed effect	Percentage disability (0 – 100). Missing scores will be imputed with a predicted score via regression of the observed PEM scores on the observed baseline MHQ scores and reference joint (MCP or PIP). If MHQ score is missing then baseline URAM score will be used in an analogous manner. If URAM is also missing then the reference joint strata specific mean of the observed baseline measurements will be used.
$\text{joint}_{jk}$	Designated study reference joint (MCP or PIP) of the $j$ th participant at recruitment site $k$	Binary fixed effect	Indicator variable MCP = 0, PIP = 1
$u_k$	Random intercept for recruitment site $k$	Random effect	Normally distributed with mean 0 and variance $\sigma_k^2$ . Independent across centres
$\epsilon_{ijk}$	Residual error (conditional on $b_k$ ) of the $i$ th measurement of the $j$ th participant at recruitment site $k$	Error term	$\epsilon_{jk}$ follows a multivariate normal distribution with mean 0 and covariance matrix $\Sigma_{jk}$

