#### **8.4.4 Michigan Hand Questionnaire**

Participants complete the MHQ at baseline and 12 and 24 months post treatment, and their scores used to generate 6 scale scores and an overall score. Only MHQ data relating to the reference hand will be analysed and reported. Descriptive statistics for MHQ scores will be reported by treatment group for each time point.

The overall score for the reference hand at each time point will be analysed using a similar covariance pattern model as used for the primary analysis, with the estimated differences in means (and two-sided 95% CIs) at each time point being reported. This model will include participants with an MHQ score for at least one post-randomisation time point (i.e. those with no post-randomisation MHQ measurements will be excluded). Any missing baseline MHQ scores will be imputed with predicted values via regression of the observed baseline MHQ scores on observed baseline PEM scores and study reference joint (MCP or PIP). If baseline PEM score is also missing then missing baseline MHQ scores will be imputed with predicted values via regression on the observed baseline URAM scores and reference joint. If baseline URAM score is also missing then missing baseline MHQ scores will be imputed with the reference joint strata specific mean.

The fitted model will be checked using the same techniques used for the primary analysis. Should any of these diagnostics suggest serious violation of the model assumptions, then the outcome data will be log transformed (with a value of 0.1 added to scores prior to transformation to allow for scores of 0) and the model refitted. If serious violation of the model assumptions persists, then the MHQ scores at each post-treatment time point will be modelled in isolation, using a univariate mixed effect linear regression models, adjusting for allocation, reference joint type (the stratification factor) and baseline MHQ score as fixed effects, and centre as a random effect. Mixed effect generalised linear models with log link will be used if model assumptions remain severely violated.

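### Appendix C contradicts itself on which MHQ aesthetics item is reverse scored, and does not say whether its no-pain rule or its missing-item rule comes first

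*SAP*

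**What the plan says.** Appendix C sets out the MHQ scoring in bullets followed by a table.

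- **Reversal, aesthetics:** "The second item in the aesthetics scale for each hand (MHQ43 and MHQ47) is reverse scored". The table gives the right-hand items as 43, 44, 45, 46 and the left-hand items as 47, 48, 49, 50.
- **Reversal, pain:** "The second item in the pain scale for each hand (MHQ34 and MHQ39) is reversed scored". The table gives pain items 33 to 37 and 38 to 42.
- **Missing items:** "If 50% or more of the items in a given scale are missing then a score for this scale cannot be validly calculated". Below that threshold, blanks take the mean of the answered items.
- **Pain special case:** the table sets the pain score to 0 when item 33 (right) or item 38 (left) equals 5, with no condition on the other items. A footnote adds: "For pain scale a higher score indicates more pain".
- **Total:** "A total MHQ score is obtained by taking the mean of the six scale scores, after reversing the score for the pain scale". A further footnote says: "The total MHQ score will be considered missing if any of the six scale scores are missing".

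On use, Section 8.4.4 says: "The overall score for the reference hand at each time point will be analysed using a similar covariance pattern model". Table 2 in Section 8.2.3 uses baseline MHQ as first choice when baseline PEM is absent: "Missing scores will be imputed with a predicted score via regression of the observed PEM scores on the observed baseline MHQ scores". Table 3 in Section 8.3.1 includes baseline and post-treatment MHQ in the imputation model.

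**The concern.** For aesthetics, the position given in the bullet and the item numbers beside it point to different questions. Two programmers could each follow Appendix C faithfully and produce different scores. The pain bullet has the same form, and there the position and numbers agree with the table, so a broken table is not the explanation.

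Reversing the wrong item does more than add noise. It leaves the oppositely worded item uncorrected and flips one that was already the right way round, so half of a four-item scale runs against the other half. The affected results would be the aesthetics scale, summarised in its own right, and the overall MHQ score, which is modelled at 12 and 24 months.

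For pain, two rules can apply to the same respondent and give different results (a score of 0, or missing). Appendix C does not say which comes first.

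**Working it through.** **Inputs, all from Appendix C.** Reversal maps an answer r to 6 − r. Aesthetics score = (25/4)(x − 4), where x is the sum of four items after reversal. The total is the mean of six scales.

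**The table's own range.** x = 4 gives 0 and x = 20 gives 100, so the stated 0 to 100 range reproduces. The problem lies in which item is reversed before x is formed.

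**Difference between the readings.** Write a43 to a46 for the right-hand answers. The left hand is identical with 47 to 50.

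- Reverse 43: x = (6 − a43) + a44 + a45 + a46
- Reverse 44: x = a43 + (6 − a44) + a45 + a46
- First minus second: 2(a44 − a43) in x, so (25/4) × 2 × (a44 − a43) = 12.5 × (a44 − a43) on the scale

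With answers from 1 to 5, a44 − a43 runs from −4 to +4. The scale difference therefore runs from −50 to +50, and the difference in one respondent's total from −50/6 to +50/6, or ±8.3. Of the 5⁴ = 625 possible answer patterns, 80% score differently under the two readings. The other 20% have a43 = a44 and score the same. This counts patterns, not respondents.

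| Answers to 43–46 | Reverse 43 | Reverse 44 |
|---|---|---|
| 1, 5, 5, 5 | 100 | 50 |
| 5, 1, 5, 5 | 50 | 100 |
| 2, 4, 4, 4 | 75 | 50 |
| 5, 5, 5, 5 | 75 | 75 |

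**Effect of choosing wrongly.** Assume that one item is worded opposite to the other three, as a single reversal per hand implies. Take a respondent who answers consistently at level v, giving 6 − v to the opposite item.

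- Right item reversed: x = 4v, score 25(v − 1), that is 0, 25, 50, 75 or 100
- Wrong item reversed: x = 2(6 − v) + 2v = 12, score (25/4) × 8 = 50 for every v

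The result is the same whichever of 43 and 44 is the correct item. If everyone answered consistently, a true between-arm aesthetics difference of D would vanish and the difference in the total would lose D/6.

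**Pain.** Take item 33 (38) = 5, with some of the other four items blank.

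| Blank items | Share of five | Missing-item rule first | Special case first |
|---|---|---|---|
| 0 to 2 | 0 to 40% | 0 | 0 |
| 3 | 60% | pain and total missing | 0 |
| 4 | 80% | pain and total missing | 0 |

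A pain score of 0 enters the total as 100. The two orders differ only with three or four blanks.

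**The case against.** The best defence is that this is a slip in an appendix, that the Trial Statistician holds the annotated CRFs (Section 7.2.1), and that the right item would be found when the scoring is programmed. That may well happen. It does not make Appendix C usable as written, because nothing in the SAP says which item is meant.

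On pain, the special case carries no condition and adds little unless other items are blank or inconsistent with item 33. That suggests it is meant to override the missing-item rule. This is a fair reading and probably the intended one, but the bullets place missing-item handling before normalisation and no sentence gives precedence.

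Four stronger inferences are tempting, and the SAP does not support them:

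- **That every respondent's score is distorted.** Scores agree whenever items 43 and 44 have equal answers, and otherwise can differ in either direction.
- **That 8.3 points is a bias in the treatment comparison.** It is the extreme for one respondent. Both arms are scored alike, so the expected effect is attenuation.
- **That pain-free respondents are lost.** This needs the missing-item rule to be applied first and respondents to leave the other items blank. The SAP establishes neither.
- **That the primary result is at risk.** Observed PEM scores, the 6-point margin and the 12-month comparison do not use MHQ. Baseline MHQ serves only to predict a missing baseline covariate, with URAM and then the stratum mean as fallbacks. In multiple imputation it is one variable beside PEM, URAM and joint measurements. A mis-scored MHQ mainly weakens those predictions.

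**Conclusion.** The aesthetics contradiction is certain from Appendix C alone. Which item is correct cannot be settled from the SAP, and a guess that the wording was carried over from the pain bullet would not settle it either. The size is 12.5 × (item 44 − item 43) on the aesthetics scale, bounded by 50 points there and 8.3 points on one respondent's total. The attenuation result assumes that one item is worded opposite to the other three and that respondents answer consistently. It bears on a modelled secondary outcome for which the SAP sets no margin, so no decision rule depends on it.

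The pain issue is a lesser one: an unstated order between two rules, which matters only with item 33 (38) = 5 and three or four other pain items blank. How many respondents that describes is not known from the document. If they were set to missing, the missingness would depend on a good outcome, which is reason enough to state the order.

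**What to change.** In Appendix C:

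1. Check against the annotated CRF which aesthetics item is worded opposite to the other three. Name it by its verified number for each hand, with a position that matches the table. Section 5.3 describes 63 questions while the table numbers items 1 to 62, so check the numbering itself at the same time.
2. State that the rule setting pain to 0 when item 33 (38) = 5 is applied before the rule that makes a scale missing at 50% or more blank items.
3. Check that the scoring code does both, for example by running the patterns tabulated above through it.

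The cost is two lines of text and one code check. No design feature or data collection changes.
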